#### **16.2.1.2 Group 2 “LOW RISK” patients:**

The primary aim of the study is to compare the reactivation free survival rate in initial responders at week 6 with continuation treatment for 6 months (Arm LR 6) versus 12 months (Arm LR 12) in those patients without disease reactivation within the first 6 months.

If the null hypothesis is true, the reactivation rate of both randomized arms are equal. If the alternative hypothesis is true, there is a difference between the two arms in terms of reactivation frequency.

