## **16.3 ANALYSES**

The analyses of the primary and secondary endpoints will be done according to the intention-to-treat principle, i.e. the patients will be analyzed in their allocated treatment group, even in case of non-compliance or protocol violations.

The statistical analyses of the primary endpoint will be done with a two-sided significance level of 5 %. The statistical analyses of the secondary endpoints are exploratory. A separate analyses will be performed for each group (“RISK” and “LOW RISK”). In addition to the intention-to-treat analyses a secondary per protocol analyses will be done including all patients who were treated according to the originally assigned treatment arm without protocol violations (= unjustified dose modification, therapy delay and/or improper switch to another therapy within the first 12 months).

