#### **16.3.1.2 Group 2 “LOW RISK” patients:**

Reactivation (=progression in any organs) and death will be considered as events for the calculation of Reactivation Free Survival. The interval will start 6 months after therapy start, i.e. the time point when half of the patients are intended stop the continuation therapy (Arm LR6) whereas patients from the other randomized arm (Arm LR12) will further receive 6 months of continuation therapy. This means, randomized patients with reactivations within the first 6 months after randomization will not be included in the analyses. For censored patients the interval will be calculated until the date of the last response evaluation.

The proportion of reactivation free survival will be estimated according to the method of Kaplan-Meier and confidence intervals according to Dorey and Korn will be given for the reactivation free survival rate after 2 and 3 years. The primary statistical evaluation of the treatment effect will be done by log rank-test.

As a secondary aim the question whether a prolonged therapy can slow down the speed of reactivation will be considered. Retrospective data from LCH-I and LCH-II and the DAL-studies indicate that the hazards between 6 and 12 months of continuation therapy are proportional and constant in time (i.e. exponentially distributed reactivation free survival times). Therefore, a Weibull accelerated failure time model will be fitted to evaluate an acceleration factor. Moreover, a time dependent Cox regression model will be performed.

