### **16.5.2 Group 2 “LOW RISK” patients:**

Data from the previous LCH-II study indicate that the reactivation free survival rate of the control group (LR 6) is approximately exponential distributed with a 1-year reactivation free survival rate of about 65%. With this study we aim to show a 20% difference in the 1-year reactivation free survival rate (i.e. a 1-year reactivation free survival rate of 85% in patients with 12 month continuation treatment) with sufficient power.

To show a 20% difference at the 5% significance level with a power of 80% we would need a total of 36 events following the group sequential design (Jennison Turnbull).

85% of the patients with multi-system LCH without involvement of risk organs had an initial response. That means that with the expected annual recruitment of 40 multi-

[figure not shown]
system patients without risk organ involvement we can expect 34 patients per year who will be eligible for randomization. We expect that 85% of these patients will be randomized this means there will be 29 randomizations/year. About 5% of these patients will show a reactivation within 24 weeks of treatment, another 10% will possibly be lost to follow up within the first 24 weeks. Thus we will be able to recruit about 24 patients/year who will enter the analyses.

We considered a cautious estimated lost to follow up-rate in the calculation, which is assumed to be exponentially distributed with  $\lambda=0.664$ , i.e. about half of the patients are followed for more than one year. Given this lost to follow up rate and a minimum follow up of 2 years (period from entry of the last patients to the final analysis) following the group sequential design, we will need a recruitment period of about 6 years and a maximum sample size of 148 patients.

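### Group 2's Weibull acceleration factor only re-expresses the hazard ratio, so it cannot tell slower from fewer reactivations; a Cox model split at month 12 would be more informative

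*Protocol*

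**What the plan says.** Section 16.2.1.2 sets the primary aim of Group 2 as a comparison of RFS between LR 6 and LR 12. The null hypothesis is worded as equal reactivation rates, and the alternative as follows: "If the alternative hypothesis is true, there is a difference between the two arms in terms of reactivation frequency".

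Section 16.3.1.2 starts the clock six months after therapy start, when LR 6 stops and LR 12 has six more months of treatment to come. The primary test is the log-rank test. Kaplan-Meier RFS with confidence intervals is planned at 2 and 3 years.

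The same section adds a second question: "As a secondary aim the question whether a prolonged therapy can slow down the speed of reactivation will be considered". Its premise is that earlier data "indicate that the hazards between 6 and 12 months of continuation therapy are proportional and constant in time", that is, that the times are exponential. The conclusion drawn is: "Therefore, a Weibull accelerated failure time model will be fitted to evaluate an acceleration factor". A time-dependent Cox model is mentioned in the next sentence.

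Section 16.5.2 describes RFS in LR 6 as "approximately exponential distributed with a 1-year reactivation free survival rate of about 65" per cent, targets 85% in LR 12, and allows for early attrition: "About 5% of these patients will show a reactivation within 24 weeks of treatment".

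**The concern.** The plan poses two questions, whether reactivations differ in frequency and whether they come more slowly, but the model named for the second estimates the same contrast as the test for the first. A significant log-rank result with an acceleration factor above 1 could be reported as two findings when it is one.

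The premise also fits the clock poorly. During its first six months one arm is treated and the other is not. If treatment suppresses reactivation only while it is given, the LR 12 hazard steps up at month 12 from therapy start and the LR 6 hazard does not. The hazards are then neither constant nor proportional, and the curves separate without any lasting gain. At stake is what may be concluded about six further months of therapy: reactivations prevented, or reactivations postponed by about the length of the extra treatment.

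**Working it through.** **1. The plan's event number.** Inputs from sections 16.3 and 16.5.2: two-sided 5%, 80% power, one-year RFS 65% v 85%.
- HR = ln 0.85 / ln 0.65 = 0.1625 / 0.4308 = 0.377.
- Fixed design (Schoenfeld): 4(1.960 + 0.842)² / (ln 0.377)² = 33.0 events.
- Five looks, O'Brien-Fleming type, with inner boundaries from the second look: inflation factor 1.127, so 33.0 × 1.127 = 37.2. The plan states 36. The same factor takes Group 1 from 202 to 228, as stated.

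The event number is not in dispute.

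**2. Acceleration factor and hazard ratio.** In a two-arm Weibull model with shape k, AF = HR^(−1/k), so AF = 1 exactly when HR = 1. With the plan's constant hazards k = 1, and AF = 1/0.377 = 2.65. Other shapes only rescale the same contrast: 4.03 at k = 0.7 and 1.92 at k = 1.5.

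**3. Slower or fewer?** I simulated 148 patients with 6-year accrual, 2 years' minimum follow-up and loss hazard 0.664/year (2,000 trials per scenario). Log-rank and Weibull reached the same decision in 94–98% of trials.
- *Fewer, not slower.* Assume 56% of LR 6 patients ever reactivate. This borrows the two-year figure after NAD in section 2 as a plateau. For one-year RFS of 65%, 0.35/0.56 = 0.625 of those must reactivate within a year. With the same timing in LR 12, one-year RFS of 85% needs 0.15/0.625 = 24% ever to reactivate. The Weibull test rejects in 84%, with median AF 4.0.
- *Postponed, not fewer.* No LR 12 events for six months, then the LR 6 process. The Weibull test rejects in 47%, with median AF 1.5.

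The acceleration factor is larger where nobody's reactivation is slowed than where every reactivation is postponed.

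**4. On-therapy and off-therapy hazards.**
- LR 6 after stopping: −ln 0.65 = 0.431/year.
- On therapy: −ln 0.95 / (24/52) = 0.111/year; 0.148/year if the window is 18 weeks (week 6 to week 24).

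The second figure comes from an allowance for the first 24 weeks. The protocol gives no hazard for months 6–12, so it is an assumption here, with a range.

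**5. Delay only.** LR 12 has hazard h for 0.5 year and then 0.431, the same as LR 6. For h = 0.111, one-year RFS = exp(−0.0555 − 0.2154) = 76%, against 65%. That is 11 of the 20 target points. At 2 years it is 50% v 42%, and at 3 years 32% v 27%.

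Share of trials in which the log-rank test at 36 events favours LR 12:

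| Assumed LR 12 hazard, months 6–12 | Favours LR 12 |
|---|---|
| 0.431 (arms equal) | 2.4–2.9% |
| 0.215 (halved) | 12–14% |
| 0.148 | 20–21% |
| 0.111 | 25–26% |
| 0 | about 47% |

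The ranges cover separate simulation runs, with and without the interim boundaries.

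**6. Splitting at month 12 from therapy start.** With no LR 12 events before month 12 and equal hazards afterwards, a log-rank test restricted to the later window rejects in 5%. Under the design alternative it rejects in 56%. About 20–25 of the 36 events fall in that window.

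**The case against.** The strongest reply is that the primary aim is RFS and the trial is sized on it. Under pure delay the RFS curves truly differ, so a log-rank rejection is correct for the stated endpoint. This stands. A reader might infer that the primary test is invalid or that 12–47% is an inflated type I error; the protocol does not support that. What remains is narrower: the word *frequency* in the alternative hypothesis claims more than the test shows.

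Second, an acceleration factor is a ratio of time scales and does measure speed if the model is true. This also stands, so it would be too strong to say that the model cannot address speed. The defect is that it cannot be told apart from the primary effect. Section 16.3 makes secondary analyses exploratory, which limits the harm.

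Third, section 16.3.1.2 already plans a time-dependent Cox model and 2- and 3-year Kaplan-Meier rates, either of which could show a fading effect. The Cox term may properly be defined in the statistical analysis plan, so its absence here is no fault. The fault is that the protocol names an uninformative model for the question and rests it on a doubtful premise.

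Fourth, the 5% is an attrition allowance, and the earlier-study data behind the constant-hazard statement are not shown. Section 2 also reports, without randomisation, 27% reactivation after 12 months of therapy against 53% and 62% after 6 months, which points away from a delay-only effect. A reader might infer that the protocol's figures refute constant hazards. They only make them doubtful.

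**Conclusion.** The point holds as a limited one about analysis choice and wording. The equivalence of the acceleration factor and the hazard ratio is algebraic and depends on no scenario: under the plan's own premise the speed analysis returns 1/HR and adds nothing to the primary contrast.

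The second part depends on assumptions. If therapy suppresses reactivation in months 6–12 and has no lasting effect, the log-rank test favours LR 12 in about 12% of trials (hazard halved) to 47% (hazard zero), and in about 25% at the rate implied by the 24-week allowance. These figures assume 148 patients, exponential loss at 0.664/year and equal hazards after month 12. They show how far a significant RFS difference can arise without a lasting reduction. They are not error rates, and they do not suggest that delay-only is the likely truth. The log-rank test remains valid for RFS.

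**What to change.** In section 16.3.1.2:

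1. Make the already planned time-dependent Cox model the analysis of the secondary aim, in place of the Weibull acceleration factor. Split it at month 12 from therapy start. Report the LR 12/LR 6 hazard ratio with confidence interval for months 6–12 (LR 12 on therapy, LR 6 off) and after month 12 (both off).
2. Do not rest the model on constant, proportional hazards.
3. Keep the log-rank test as the primary test, but word its conclusion as RFS, read alongside the two hazard ratios and the planned 2- and 3-year Kaplan-Meier rates. Align the alternative hypothesis in section 16.2.1.2 with that wording.

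The cost is wording only, with no new data or patients. With about 20–25 events after month 12, the later hazard ratio will be imprecise and is for estimation, not for a decision.

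A stricter rule may be tempting: claim fewer reactivations only if the 2-year Kaplan-Meier difference is also significant. I advise against it. With one analysis at 36 events, log-rank plus that condition succeeds in 59% of trials under the design alternative (log-rank alone 80%). In a lasting-benefit case (0.111 then 0.214/year) it succeeds in 49% (alone 78%). With the interim boundaries the figures are 47% and 38%, against about 75%. Only about 5 to 9 patients per arm are at risk at 2 years. The rule would not isolate delay either, since RFS still differs then (50% v 42% in step 5).

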### **16.3.2 Analysis of secondary endpoints**

The overall survival time will be calculated from the date of randomization to death or the last response evaluation.

The reactivation free survival will be calculated from the date of initial response evaluation at week 12. Reactivation (=progression overall and in risk organs after response at week 12) and death will be considered as events. For censored patients the interval will be calculated until the date of the last response evaluation.

The time to non active disease (NAD) will be calculated from randomization to the date of NAD. For censored observation the interval will be calculated until the date of the last follow up information.

The reactivation free survival after NAD will be calculated from the date of NAD. Reactivation (reappearance or progression in any organ) and death will be considered as events. For censored patients the interval will be calculated until the date of last response evaluation.

The time to permanent consequences will be calculated from the date of randomization to the diagnoses of permanent consequences. Deaths without permanent consequences will be censored at the time of death. For all other censored patients the interval will be calculated until the date of the last response evaluation. For the comparison of treatment arms patients with permanent consequences which are already

present at therapy start will not be considered in the analyses.

The proportion of survival, reactivation free survival after response in week 12, reactivation after NAD, the time to NAD and the incidence of permanent consequences will be estimated by the method of Kaplan Meier. The comparison of the randomized arms will be done by log rank-tests.

The proportion of patients with severe organ toxicity (WHO score grade III-IV) within the first 12 weeks of treatment will be compared with Fisher's exact test.

To study the effect of prolonged initial therapy in Low Risk patients without response at week 6. the response rate at week 12 (compared to the status of disease at week 6) will be compared to the response rate at week 12 of the corresponding LCH-II patients. This will be done with Fisher's exact test.

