## **6 GOALS FOR LCH III**

Like in the LCH II study the overall aims of this study are:

- to deliver risk-adapted therapy according to the extent and severity of the disease
- to evaluate the response in the different patient groups
- to evaluate the rate of failure in the different treatment groups, i.e. nonresponse to therapy or disease reactivation during therapy
- to assess morbidity, i.e. evaluation of therapy toxicity and evaluation of the incidence of permanent consequences in the different treatment groups.

The specific goals for the 3 patient groups are as follows:

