#### **16.2.2 Secondary endpoints**

- Overall survival
- Proportion of responders (overall and in risk organs) at week 6
- Proportion of responders (overall and in risk organs) at week 12
- Reactivation free survival after response at week 12
- Time to NAD
- Incidence of permanent consequences
- Toxicity
- Reactivation free survival after NAD (overall and in risk organs) and for “RISK” patients a historical comparison of Arm A of LCH III with Arm A of LCH-II with respect to the frequency of reactivation to evaluate the impact of the

prolonged study duration in risk patients

- Value of a prolonged initial treatment (course 2) of non-responding “LOW RISK” patients compared to a historical control of LCH-II patients without “RISK” organ involvement

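### Group 1 reactivation is compared between arms only in patients who responded or reached NAD, an outcome arm B is meant to change, and no endpoint from randomisation combines non-response and reactivation

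*Protocol*

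**What the plan says.** Section 16.2.2 lists "Reactivation free survival after response at week 12" among the secondary endpoints, together with reactivation free survival after NAD. Section 16.3.2 sets the time origins. For the first: "The reactivation free survival will be calculated from the date of initial response evaluation at week 12". For the second: "The reactivation free survival after NAD will be calculated from the date of NAD". Death and reactivation are events in both. The same section includes both in the list that ends: "The comparison of the randomized arms will be done by log rank-tests".

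Section 16.3 adds: "The analyses of the primary and secondary endpoints will be done according to the intention-to-treat principle". It explains this as analysis in the allocated group despite non-compliance or protocol violations. It also says: "The statistical analyses of the secondary endpoints are exploratory".

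The Group 1 primary endpoint (section 16.2.1.1) is the proportion of non-responders in risk organs, with death within 12 weeks counted as non-response. Section 16.5.1 plans for 50% non-response in arm A and 30% in arm B.

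Among the overall aims in section 6 is "to evaluate the rate of failure in the different treatment groups, i.e. nonresponse to therapy or disease reactivation during therapy".

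**The concern.** Randomisation makes the arms comparable at entry. It does not make the week-12 responders of one arm comparable with those of the other when treatment affects who responds. If the trial succeeds as planned, arm B's responders include a group who would have failed on arm A. Section 2.1 names response to initial treatment as one of the most important prognostic factors, so these extra responders may well be a poorer-risk group. Arm B could then show more reactivation among responders although methotrexate does no harm to anyone's later course. If methotrexate lowered response, the selection would run the other way. The after-NAD comparison has the same structure, although the protocol plans no figure for NAD by arm.

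The comparison will be read. Arm B continues oral methotrexate through month 12 (section 9.1.2.3), so readers will look to reactivation for its benefit. The text under Figure 6 in section 16.4 also lists reactivation among the considerations for stopping or continuing once the inner boundary is crossed.

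No listed endpoint counts non-response, reactivation and death together from randomisation. Overall survival and time to NAD start there, but neither counts reactivation.

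**Working it through.** **The plan's own figures.** The protocol gives no power or event number for the reactivation endpoints, so there is none to reproduce. The Group 1 sample size, which supplies the response rates used here, does reproduce. With 50% against 30% non-response, equal allocation (assumed) and a two-sided 5% Fisher test, exact power is 79.9% at 101 per arm and 80.6% at 102 per arm; the protocol states 202 in total. A five-look two-sided O'Brien-Fleming-type design with stopping for the null inflates 202 to 227.5, with expected sizes of 143.2 and 158.2; the protocol states 228, 143 and 158.

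**Inputs for the illustration.**
- Response at week 12: A = 1 − 0.50 = 0.50; B = 1 − 0.30 = 0.70 (section 16.5.1).
- Assumed: everyone who responds on A would also respond on B. The extra 0.70 − 0.50 = 0.20 of arm B respond only because of B.
- Reactivation by 2 years in patients who respond on either arm: q = 0.64. This is the LCH II after-NAD figure for risk patients (section 2), borrowed here for week-12 responders.
- Reactivation in patients who respond only on B: r, not given in the protocol. Assumed range 0.64 to 1.00.
- Assumed: methotrexate has no effect on later reactivation.

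**Among responders only.** A = q = 0.64. B = (0.50 × 0.64 + 0.20 × r) / 0.70.
- r = 0.64: (0.320 + 0.128) / 0.70 = 0.640
- r = 0.90: (0.320 + 0.180) / 0.70 = 0.714
- r = 1.00: (0.320 + 0.200) / 0.70 = 0.743

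**Failure from randomisation (non-response or reactivation).** A = 0.50 + 0.50 × 0.64 = 0.82. B = 0.30 + 0.50 × 0.64 + 0.20 × r.
- r = 0.64: 0.748
- r = 0.90: 0.800
- r = 1.00: 0.820

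At r = 0.90, B looks 7 points worse among responders and is 2 points better in all randomised patients.

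**A lower base rate.** Section 2 gives 27% reactivation after 12 months of therapy in the DAL-HX studies (all multisystem patients). With q = 0.27:
- r = 0.64: responders 0.270 in A against (0.135 + 0.128) / 0.70 = 0.376 in B; failure from randomisation 0.635 against 0.563.
- r = 0.90: responders 0.270 against (0.135 + 0.180) / 0.70 = 0.450; failure from randomisation 0.635 against 0.615.

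The gap among responders is therefore 0 to 18 points against B over q = 0.27 to 0.64 and r = 0.64 to 0.90. Failure from randomisation favours B by 2 to 7 points over the same range.

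**What the log-rank test would do.** Trials were simulated with 114 per arm, 2-year follow-up, exponential reactivation times within each patient class and no true effect on reactivation. The nominal rate of calling B significantly worse is 2.5%.

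| q / r | Responders only: B significantly worse | From randomisation: B significantly worse |
|---|---|---|
| 64% / 64% | about 2% | 0.1% or less |
| 64% / 90% | about 17 to 18% | 0.1% or less |
| 50% / 80% | about 17 to 18% | 0.1% or less |

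The first row confirms that the bias disappears when prognosis is equal.

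**The case against.** Several counter-arguments stand and limit the point.

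- **The bias is conditional.** It needs a worse reactivation prognosis in patients who respond only on B. A reader might infer that the comparison must be biased against B if methotrexate works. The protocol gives no figure that supports this, and at equal prognosis the bias is zero.
- **The failure aim.** A reader might infer that it has no endpoint. It does: non-response is the primary endpoint and reactivation has the conditional endpoints. Section 6 also speaks of evaluating, not comparing, and limits reactivation to the treatment period. Only a combined endpoint is absent.
- **The morbidity goal.** A reader might infer that it cannot be assessed. Section 6.1.2 ties that goal to longer continuation, which both arms receive. Section 16.2.2 addresses its reactivation part by a historical comparison of arm A in LCH III with arm A in LCH II. Permanent consequences are timed from randomisation.
- **Intention to treat.** A reader might see a contradiction with section 16.3. As defined there, the principle means analysis in the allocated group, and reactivation after response has no meaning in patients who never responded. The label does not make the comparison a randomised one, but the text does not contradict itself.
- **The inputs fit loosely.** The 64% is an after-NAD rate from 6 months of therapy, in a risk group that also included children under 2 without risk organs. Any benefit of continued oral methotrexate is left out. That B is never worse on failure from randomisation follows from the set-up, since the extra 20% cannot fail more than completely.
- **Consequences are limited.** These endpoints are exploratory. The role of reactivation in the stopping discussion is one consideration among several, and at an inner-boundary crossing the response difference, and so the selection, may be small.

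None of this changes the fact that the stated test compares sets of patients selected by an outcome that treatment is designed to change.

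**Conclusion.** The point holds as a minor one. The two Group 1 reactivation comparisons are conditional on post-randomisation success and cannot be read as randomised effects of methotrexate. Under the planned response rates and assumed reactivation rates, responders show 64% in A against 64% to 74% in B, while failure from randomisation is 82% against 75% to 82%. The direction can therefore reverse. These figures rest on a borrowed base rate, an unquantified prognosis in patients who respond only on B, and no methotrexate effect on later reactivation. They show direction, not an expected size. The two parts of the failure aim are covered separately, and what is missing is one endpoint from randomisation that combines them.

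**What to change.** Add to sections 16.2.2 and 16.3.2, for Group 1, failure-free survival from randomisation in all randomised patients. Events are non-response as defined in section 16.2.1.1, later reactivation, and death. Compare the arms on this endpoint, report the 12-month rate so that it matches the treatment-period wording of the aim in section 6, and tabulate the components by arm.

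Keep the curves after week-12 response and after NAD, labelled as descriptive, non-randomised comparisons.

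The cost is a wording change and one more survival analysis on data already collected. The drawback is that the composite is driven largely by the week-12 primary endpoint: in the illustration, non-response makes up 0.50 of the 0.82 failures in arm A, or 61%. The component table is needed for that reason.

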#### **8.2.2 Eligibility for randomization 2 “LOW RISK” patients**

- eligibility for the study
- multisystem disease without involvement of “RISK” organs
- response to initial therapy, i.e. regression (AD better) or resolution (NAD) after 6 weeks of initial treatment course 1

Randomisation will be performed by the study subcenter or study reference center promptly after the reception of the registration, diagnostic evaluation or follow up and consent forms. The information on the assigned treatment arm and the randomisation number will be forwarded to the participant by e-mail or fax without delay.

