## 16.1 DESIGN

### 16.1.1 Group 1 “RISK” patients

The Group 1-Study of LCH-III is a randomized controlled clinical trial for patients with multi-system LCH WITH involvement of “RISK” organs (hematopoetic system, liver, spleen or lungs). The random assignment to the treatment arms will be done in blocks, stratified according to local subcenters to ensure a balance within the local subcenters and within each pre-specified number of treatment assignments (=block). The randomization will be done in the local subcenter without delay after diagnosis.

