### 16.1.2 Group 2 “LOW RISK” patients:

The Group 2-Study of LCH-III is a randomized controlled clinical trial for patients with multi-system LCH WITHOUT involvement of “RISK” organs (hematopoetic system, liver, spleen or lungs) and initial response at week 6 (NAD/AD better).

The random assignment to the treatment arms will be done in blocks stratified according to age at diagnosis ( $\leq 2$  years,  $> 2$  years) and local subcenters to ensure a balance within age groups, the local subcenters and within each pre-specified number of treatment assignments (=block). The randomization will be done in the local subcenter without delay after the first response evaluation 6 weeks after therapy start. Only patients with therapy response, i.e. regression (AD better) or resolution (NAD) after 6 weeks of initial treatment, will be eligible for randomization.

In addition, the impact of a prolonged initial treatment (= course2) for those patients who are not eligible for randomization is examined and compared with the historical control group of LCH-II patients.

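### Time to NAD and time to permanent consequences start at randomisation, which in Group 2 comes after week 6, so some counted events precede the clock

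*Protocol*

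**What the plan says.** Protocol section 16.3.2 fixes the origin of two secondary endpoints. For the first: "The time to non active disease (NAD) will be calculated from randomization to the date of NAD". For the second: "The time to permanent consequences will be calculated from the date of randomization to the diagnoses of permanent consequences". Neither sentence distinguishes the groups. For the arm comparison of permanent consequences, the section leaves out patients whose consequences are already "present at therapy start will not be considered in the analyses". Both endpoints are to be estimated by Kaplan-Meier and the arms compared by log-rank test.

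Section 16.3 applies the analyses to the RISK and LOW RISK groups in turn: "A separate analyses will be performed for each group". The list of secondary endpoints in 16.2.2 does not confine these two to Group 1, and section 6.2.1 names fewer permanent consequences as a Group 2 goal.

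The groups are randomised at different times. For Group 1, section 16.1.1 says: "The randomization will be done in the local subcenter without delay after diagnosis". For Group 2, section 16.1.2 says: "The randomization will be done in the local subcenter without delay after the first response evaluation 6 weeks after therapy start". Section 8.2.2 makes eligibility for the Group 2 randomisation depend on "response to initial therapy, i.e. regression (AD better) or resolution (NAD) after 6 weeks of initial treatment course 1", and has randomisation performed "promptly after the reception of the registration, diagnostic evaluation or follow up and consent forms". The response table in 10.3.2 likewise sends both NAD and AD-better patients to randomisation at week 6.

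**The concern.** A clock that starts at randomisation suits an endpoint that can occur only after randomisation. That is broadly so in Group 1, which is randomised at diagnosis. In Group 2 about six weeks of treatment come first, and both endpoints can occur in that time. For NAD this is no rare accident, because reaching NAD by week 6 is an entry route to the randomised comparison.

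The two endpoints fail for different reasons. Time to NAD fails because the randomised set includes patients who already have the event. Time to permanent consequences fails because its exclusion date (therapy start) and its clock (randomisation) lie about six weeks apart. Being NAD at week 6 has no bearing on the second problem.

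At stake is what the Group 2 curves and log-rank tests mean. The protocol does not say how a time of zero or less is to be treated. An analyst could keep such patients as events at or before time zero, set their times to a small positive value, or leave them out, and the Kaplan-Meier estimates would differ. However they are handled, these events precede allocation and cannot reflect 6 versus 12 months of treatment.

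**Working it through.** **Order of dates in Group 2**

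The rule is: time = date of event − date of randomisation. The day numbers below are illustrations, counted from therapy start.

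| Group 2 patient | Event | Randomised | Time under 16.3.2 | In the arm comparison? |
|---|---|---|---|---|
| NAD at week 6, randomised the same day | day 42 | day 42 | 42 − 42 = 0 | yes |
| NAD at week 6, randomised three days later | day 42 | day 45 | 42 − 45 = −3 days | yes |
| Consequence first diagnosed in week 4 | day 28 | day 45 | 28 − 45 = −17 days | yes, because absent at therapy start |
| AD better at week 6, NAD at week 14 | week 14 | week 6 | 14 − 6 = 8 weeks | yes, and valid |

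Rows 1 and 2 cover every patient who qualifies through NAD. The follow-up form that documents the response has to arrive before randomisation, so the date of NAD cannot be later than the randomisation date. Row 3 covers any consequence first diagnosed between therapy start and randomisation. Row 4 is no error: randomisation is a proper origin for comparing randomised arms.

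**Group 1 for contrast**

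Randomisation follows diagnosis without delay, so there is no comparable treated period before the clock starts.

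**How many Group 2 patients might be affected**

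Inputs from section 16.5.2: 40 multisystem patients a year without risk organ involvement, 85% initial response, 85% of responders randomised, 5% reactivating and 10% lost within the first 24 weeks, recruitment of about 6 years, maximum sample size 148.

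First the plan's own figures:
- Eligible: 40 × 0.85 = 34 a year, as stated.
- Randomised: 34 × 0.85 = 28.9 a year, stated as 29.
- Entering the primary analysis: 28.9 × (1 − 0.05 − 0.10) = 24.6 a year, stated as about 24.
- Over 6 years: 24.6 × 6 ≈ 147, against the stated 148.

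So 148 is the number left after early reactivations and losses. A clock that starts at randomisation applies to all randomised patients, about 29 × 6 = 174.

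The protocol does not give the share who are NAD at week 6. As an assumption, over a wide range:

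| Assumed share NAD at week 6 | Patients with time to NAD ≤ 0, of 174 |
|---|---|
| 10% | 17 |
| 20% | 35 |
| 30% | 52 |
| 40% | 70 |
| 50% | 87 |

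No comparable count can be given for permanent consequences, because the protocol has no rate for the first six weeks of treatment.

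**The case against.** The best defence is that these endpoints are exploratory under section 16.3, that the Group 2 primary endpoint has its own origin six months after therapy start (16.3.1.2), and that NAD status and consequences before allocation are balanced between arms in expectation. All of that stands. It limits the importance of the point, but it does not make the stated times valid.

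A reader might infer four stronger conclusions, which the protocol does not support:

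- **That the fastest responders drop out and the NAD estimate falls.** With the LCH II LOW RISK figure of 84% eventually NAD, removing a share q gives (0.84 − q)/(1 − q), that is 80%, 77%, 73% and 68% for q of 20%, 30%, 40% and 50%. This requires the patients to be dropped, which the protocol does not prescribe, and at least one standard Kaplan-Meier implementation keeps times of 0 and −3. The 84% also belongs to another population: LCH II LOW RISK patients over 2 years of age, week-6 non-responders included. The patients randomised here are week-6 responders and include younger children without risk organ involvement.
- **That one arm is favoured.** Events before allocation add noise and dilute the contrast. Nothing shows that they fall systematically on one arm.
- **That times to NAD in Groups 1 and 2 cannot be compared.** The protocol plans no such comparison.
- **That all remaining Group 2 times are six weeks too short.** This is so only if therapy start is preferred as origin. For the randomised comparison, randomisation is legitimate.

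**Conclusion.** The point holds, limited to two exploratory secondary endpoints in Group 2. The origin is stated explicitly, so this is a rule that yields invalid times when followed, and not a detail left for a later plan. Patients NAD at week 6 enter the time-to-NAD comparison with the event already behind them. Patients with a consequence first diagnosed during initial treatment enter the other comparison with an event that precedes allocation.

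The conclusion rests only on the order of dates fixed in sections 8.2.2, 16.1.2 and 16.3.2. Its size is unknown: the 17 to 87 of 174 depend on the assumed 10% to 50% and on the planned accrual. Primary analyses, sample sizes, significance level and interim boundaries do not change. It merits a correction of the text and nothing more serious.

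**What to change.** In section 16.3.2, for the Group 2 arm comparisons:

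1. Keep randomisation as the origin of both endpoints.
2. Restrict time to NAD to patients not yet NAD at randomisation, and report by arm the proportion already NAD at week 6.
3. For permanent consequences, leave out patients whose consequences are present at randomisation, in place of therapy start.

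Both restrictions use status known before allocation, so the comparison stays randomised.

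If a descriptive time to NAD from therapy start is wanted for Group 2, it should include all Group 2 patients. Counting from therapy start among randomised patients alone would select on week-6 response. Group 1 needs no change.

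The cost is a few sentences and a smaller Group 2 set for the time-to-NAD comparison. The patients removed could not inform that comparison. The two restrictions need only the dates of randomisation, NAD and first consequence, which the present definitions already require.
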